#### 8.4.3 ADVERSE EVENT REPORTING

All reporting comply with Michigan Medicine IRB guidelines

(<https://az.research.umich.edu/medschool/guidance/adverse-event-reporting>).

Any serious adverse event that are adjudicated as being definitely or possibly related to the study intervention will be reported to the IRB within 7 calendar days of the study team becoming aware of the event.

All non-serious adverse events that are adjudicated as being definitely or possibly related to the study intervention will be reported to the IRB in aggregate at least annually.

All serious adverse events that are adjudicated as being definitely or possibly unrelated to the study intervention will be reported to the IRB in aggregate at least annually.

All non-serious adverse events that are adjudicated as being definitely or possibly unrelated to the study intervention will be collected for analysis but not reported to the IRB.

All adverse events in which the adjudication team is unable to assess the relatedness to the study intervention will be reported to the IRB in aggregate at least annually.

---

#### 8.4.4 REPORTING EVENTS TO PARTICIPANTS

Not applicable

### 8.5 UNANTICIPATED PROBLEMS

---

#### 8.5.1 DEFINITION OF UNANTICIPATED PROBLEMS (UP)

The Office for Human Research Protections (OHRP) considers unanticipated problems involving risks to participants or others to include, in general, any incident, experience, or outcome that meets **all** of the following criteria:

- Unexpected in terms of nature, severity, or frequency given (a) the research procedures that are described in the protocol-related documents, such as the Institutional Review Board (IRB)-approved research protocol and informed consent document; and (b) the characteristics of the participant population being studied;
- Related or possibly related to participation in the research (“possibly related” means there is a reasonable possibility that the incident, experience, or outcome may have been caused by the procedures involved in the research); and
- Suggests that the research places participants or others at a greater risk of harm (including physical, psychological, economic, or social harm) than was previously known or recognized.

---

#### 8.5.2 UNANTICIPATED PROBLEM REPORTING

The investigator will report unanticipated problems (UPs) to the reviewing institutional review board (IRB) and to the DSMB. The UP report will include the following information:

- Protocol identifying information: protocol title and number, PI's name, and the IRB project number;
- A detailed description of the event, incident, experience, or outcome;
- An explanation of the basis for determining that the event, incident, experience, or outcome represents an UP;
- A description of any changes to the protocol or other corrective actions that have been taken or are proposed in response to the UP.

To satisfy the requirement for prompt reporting, UPs will be reported using the following timeline:

- UPs that are adverse events will be reported to the IRB and to the study sponsor within 24 hours of the investigator becoming aware of the event.
- Any other UP (e.g., study protocol deviations) will be reported to the IRB and to the study sponsor within 2 weeks or 10 business days of the investigator becoming aware of the problem.

### 8.5.3 REPORTING UNANTICIPATED PROBLEMS TO PARTICIPANTS

Not applicable.

## 9 STATISTICAL CONSIDERATIONS

### 9.1 SAMPLE SIZE DETERMINATION

This study is powered for our primary comparison, which is the comparison of our two different notifications. We will use mixed-effects binary logistic regression to model the proportion of inappropriate DOACs that are changed within 7 days following an alert.

We anticipate randomizing 300 prescribers to different notifications over the course of the study, allowing for a main effect comparison of 150 prescribers randomized to each of Notification A vs. B. This estimate for prescribers is pulled from 2019 preliminary data indicating Michigan Medicine had more than 1000 unique DOAC prescribers, and a one-day pull in February 2020 that indicated more than 250 prescribers on that day had one or more patients currently receiving an inappropriate DOAC, thus eligible for randomization to a longitudinal notification. For our secondary aim, examining the main effect of alerts, we also anticipate randomizing 300 prescribers to initial prescription alerts over the study period, or 150 to each of Alert 1 and Alert 2, respectively.

For our patient-level main effects analyses, we estimate that prescribers will average 2 patients that trigger an inappropriate DOAC alert over the 12-month trial period. As of June 14, 2022, Michigan Medicine currently has 11,590 patients receiving a DOAC. Pilot data indicates that about 40% of prescribers changed prescriptions following an notification that did not involve a pharmacist; notifications that did involve pharmacists resulted in change approximately 60% of the time. Using a base rate of 40% and assuming a patient  $n=600$ , alpha of 0.05 and prescriber-level ICC of 0.1, we will have 80% power to detect a difference in proportions of 0.12 (or 40% vs. 52%). Table 3 shows power for several other risk ratios, baseline rates, and number of patients per prescriber. All estimates were computed in Stata 17.

Table 3. Power Calculations (Prescriber N=300)

Table 3. Power Calculations (Prescriber N=300)				
Patient n=2	Base Proportion			
Risk Ratio	0.3	0.4	0.5	0.6
1.2	32%	47%	65%	84%
1.3	44%	63%	83%	96%
1.4	67%	87%	98%	>99%
1.5	84%	97%	>99%	>99%
1.6	94%	>99%	>99%	>99%
Patient n=3				
Risk Ratio				
1.2	42%	60%	79%	94%
1.3	74%	91%	99%	>99%
1.4	93%	>99%	>99%	>99%
1.5	>99%	>99%	>99%	>99%
1.6	>99%	>99%	>99%	>99%

For our secondary prescriber-level outcomes, we will have 94% power to detect a difference in proportions of 0.4 to 0.6. For longitudinal outcomes (e.g., maintenance), this calculation is conservative as it does not account for repeated measures. For our clinical effectiveness secondary outcome, we will have 63% power to detect a difference of 1% vs. 0.5% in adverse event rates for each factor, again assuming 300 prescribers with an average of 2 patients each, and assuming a prescriber-level ICC of 0.03 (for clinical adverse events). A less conservative estimate of 3 patients per prescriber increases this power to 79%

For our exploratory moderation analyses, described below in Section 9.3.5, again assuming 300 prescribers with 2 patients each and an ICC of 0.1, we will have 80% power to detect a minimum effect size of 0.34 for our binary prescriber-level moderators, using a two-sided test with  $[\alpha] = 0.05$ . If our average number of patients per prescriber is 3, this minimum detectable effect size decreases to 0.29 under the same assumptions. For our binary cross-level (patient-level) moderators, assuming a non-randomly varying slope, with an average of 2 patients per prescriber, we will have 80% power to detect a minimum effect size of 0.34; assuming 3 patients per prescriber decreases this minimum detectable effect size to 0.27. Minimum detectable effect sizes for cross-level moderators that also include a random slope are slightly larger at 0.36 and 0.28 respectively

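### Table 3's two-patient rows for risk ratios 1.3 to 1.6 match 200 prescribers, not 300, and contradict the text's correct 80%; the moderator effect sizes do not follow from the stated inputs

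*Combined protocol and SAP*

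**What the plan says.** Section 9.1 sets out the design: "We anticipate randomizing 300 prescribers to different notifications over the course of the study". Half of them, 150, go to each notification arm. It expects that "prescribers will average 2 patients that trigger an inappropriate DOAC alert", which gives 600 patients. "Using a base rate of 40" per cent, an alpha of 0.05 and a prescriber-level ICC of 0.1, it concludes: "we will have 80% power to detect a difference in proportions of 0.12 (or 40% vs. 52" per cent).

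The table that follows is headed "Table 3. Power Calculations (Prescriber N=300"). It gives power by risk ratio and base proportion, in one block for 2 patients per prescriber and another for 3. In the two-patient block, the cell for risk ratio 1.3 and base 0.4 reads 63%.

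For the exploratory moderators, the same section again assumes 300 prescribers, 2 patients each and an ICC of 0.1, with a two-sided test: "we will have 80% power to detect a minimum effect size of 0.34 for our binary prescriber-level moderators". With 3 patients, "this minimum detectable effect size decreases to 0.29 under the same assumptions". For patient-level moderators with a non-random slope it gives 0.34 and 0.27, and with a random slope 0.36 and 0.28.

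**The concern.** A rise from 40% to 52% is a risk ratio of 0.52/0.40 = 1.3. The sentence and the table cell therefore describe one scenario with the same inputs, yet report 80% and 63%. This is the comparison on which the trial is powered, and a reader working from the table would think it well short of 80%.

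The moderator figures raise a different question. A treatment-by-moderator interaction is estimated much less precisely than a main effect, and 0.34 looks small for 300 prescribers with two patients each. Section 9.3.5 says moderators that show clinical and statistical significance will be considered for tailoring alert delivery. An optimistic minimum would therefore overstate what those analyses can find.

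**Working it through.** **Main effect and Table 3**

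Inputs from section 9.1: N = 300 prescribers split equally, m = 2 or 3 patients each, ICC = 0.1, alpha = 0.05. A two-sided test is assumed here, since the plan states sidedness only for the moderators.

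Effective patients per arm: n = (N/2) × m / [1 + (m − 1) × ICC].

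- 300 prescribers, 2 patients: 300/1.1 = 272.7.
- 200 prescribers, 2 patients: 200/1.1 = 181.8.
- 300 prescribers, 3 patients: 450/1.2 = 375.

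Power = Φ[(d − 1.96 × s0)/s1], with s0 = √[2p̄(1 − p̄)/n] and s1 = √{[p1(1 − p1) + p2(1 − p2)]/n}.

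The plan's own figure first, 0.40 vs 0.52 (d = 0.12, p̄ = 0.46):

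- 300 prescribers: s0 = 0.04268, s1 = 0.04237, (0.12 − 0.08365)/0.04237 = 0.858, power **80.5%**. The text's 80% is reproduced.
- 200 prescribers: s0 = 0.05227, s1 = 0.05189, (0.12 − 0.10245)/0.05189 = 0.338, power **63.2%**. This is the table's 63%.

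Two-patient block, base 0.3/0.4/0.5/0.6, in per cent:

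| Risk ratio | Printed | At 300 | At 200 |
|---|---|---|---|
| 1.2 | 32/47/65/84 | 31.9/46.9/65.1/84.3 | 22.8/33.6/48.3/67.7 |
| 1.3 | 44/63/83/96 | 59.9/80.5/94.5/99.6 | 43.8/63.2/82.7/96.3 |
| 1.4 | 67/87/98/>99 | 83.3/96.4/99.8/>99 | 66.5/86.6/97.6/>99 |
| 1.5 | 84/97/>99/>99 | 95.3/99.7/>99/>99 | 84.3/97.1/>99/>99 |
| 1.6 | 94/>99/>99/>99 | 99.2/>99/>99/>99 | 94.4/>99/>99/>99 |

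The 1.2 row fits 300 only. In the other four rows, all ten cells not printed as >99% fit 200 and not 300. The six cells printed as >99% hold at either number.

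The three-patient block reproduces at 300. For example, risk ratio 1.2 gives 41.6/59.8/78.7/93.6 against the printed 42/60/79/94, and risk ratio 1.3 at base 0.3 and 0.4 gives 73.7 and 91.1 against 74 and 91.

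The unpooled version of the test changes results by less than one point. At 300 prescribers, these variants do not rescue rows 1.3 to 1.6: a one-sided test, alpha 0.01, ICC 0, 0.2 or 0.3, one patient per prescriber, or a continuity correction. An ICC of 0.65 would, because 600/1.65 = 400/1.1 = 363.6 effective patients, but the stated ICC is 0.1.

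**Moderators**

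The plan gives no formula, moderator split or covariate R-squared. The check uses the standard two-level minimum detectable effect size with 1:1 allocation, a 50:50 moderator split (the most favourable), multiplier 2.81 and R-squared = 0.

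- Prescriber level: 2.81 × √{[0.1 + 0.9/m] × 16/300}. For m = 2, 2.81 × √0.02933 = 0.48. For m = 3, 2.81 × √0.02133 = 0.41. Printed: 0.34 and 0.29.
- Patient level, non-random slope: 2.81 × √[0.9 × 16/(300m)]. For m = 2, 2.81 × √0.024 = 0.435. For m = 3, 2.81 × √0.016 = 0.355. Printed: 0.34 and 0.27.

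Sensitivity to R-squared, which multiplies each value by √(1 − R²) when it is the same at both levels:

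- R² = 0.5: prescriber level 0.340 and 0.290, as printed; patient level 0.308 and 0.251.
- R² = 0.4: patient level 0.337 and 0.275, close to the printed values; prescriber level 0.373 and 0.318.

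No single R-squared gives both printed sets.

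**The case against.** The strongest reply on Table 3 is that the section's main power figures stand. The text's 80%, the risk ratio 1.2 row, the three-patient block and the 94% for prescriber-level outcomes all reproduce at 300. That is correct. A reader might infer from the 63% that the primary comparison is underpowered, or that section 9.1 as a whole was not computed for 300 prescribers. The documents support neither reading: the error is confined to four rows, and it is conservative.

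On the moderators, the reply is that the printed values may rest on covariate adjustment the plan did not spell out. Section 9.3.1 includes stratification variables and unbalanced baseline characteristics in the model, and section 9.3.5 builds the moderator tests on that model. This also stands, so 0.48/0.41 and 0.44/0.36 cannot be put forward as unconditionally right.

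A reader might also infer that the moderator figures were computed for 500 to 600 prescribers, since those numbers reproduce them without covariates. That is not established. About 600 fits the prescriber-level pair and about 500 the patient-level pair, so no one number fits both, and undisclosed R-squared values explain them equally well.

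What the reply does not remove is the conflict between text and table, or the absence of the inputs needed to obtain the moderator figures.

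**Conclusion.** The point holds in two parts of different strength.

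- **Table 3 is wrong as printed.** Ten cells in the two-patient rows for risk ratios 1.3 to 1.6 understate power, the worst by about 17 points (63% printed, 80.5% correct, in the plan's own primary scenario). This rests on the stated inputs, a two-sided test and the usual design effect. The same method reproduces the text's 80%, the 1.2 row and the three-patient block. That the values match 200 prescribers is an inference from the fit; the plan does not mention that number. The sample size is unaffected.
- **The moderator minima do not follow from what is stated.** Without covariates and at the most favourable split, they would be about 1.4 times the printed values at prescriber level (0.48/0.34) and about 1.3 times at patient level (0.435/0.34). Whether the cause is an arithmetic slip or an unstated R-squared of about 0.5 and 0.4 cannot be settled from the documents. These analyses are labelled exploratory, which limits the consequence.

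**What to change.** In Table 3, two-patient block, replace four rows with the values for 300 prescribers (base 0.3/0.4/0.5/0.6):

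- Risk ratio 1.3: 60/80/95/>99% (the third value is 94.5% before rounding)
- Risk ratio 1.4: 83/96/>99/>99%
- Risk ratio 1.5: 95/>99/>99/>99%
- Risk ratio 1.6: 99/>99/>99/>99%

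Leave the 1.2 row, the three-patient block and the 80% sentence as they are. State that the test is two-sided.

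For the moderators, either state and justify the moderator split and covariate R-squared that give 0.34/0.29 and 0.34/0.27, or restate the minima at the no-covariate values of about 0.48/0.41 and 0.44/0.36 with the 50:50 split declared. Recompute the random-slope figures (0.36 and 0.28) on whichever basis is chosen.

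The cost is a table correction and a few sentences, with no change to sample size, design or analysis.

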## 3 OBJECTIVES AND ENDPOINTS

OBJECTIVES	ENDPOINTS	JUSTIFICATIONS
Primary		
Determine the effect of notifications regarding existing DOAC prescriptions on prescriber behavior	The number (proportion) of notifications (in the existing-prescription notification conditions) that result in any prescription change within 7 days.	The goal of alerts and notifications is to bring about corrections in prescription errors. Given that “correct” is not always an absolute assessment, our primary outcome measure will capture any change to the DOAC prescription that results from the notification.
Secondary		
Determine the effect of alerts regarding newly prescribed DOACs on prescriber behavior	The number (proportion) of alerts (in the newly prescribed DOAC alert conditions) that result in any prescription change within 7 days.	The goal of alerts and notifications is to bring about corrections in prescription errors. Given that “correct” is not always an absolute assessment, our primary outcome measure will capture any change to the DOAC prescription that results from the notification.
	Change in magnitude of effect for the existing-prescription notification over time. This is reported on at the institution level (not individual level).	The effectiveness of notifications should be sustained over time. This measure examines longitudinal trends in effectiveness.

	(This outcome measure analysis is based on the primary outcome)	
	Change in magnitude of effect for the new-prescription alert over time, reported on at the institution level (not individual level).	The effectiveness of alerts should be sustained over time. This measure examines longitudinal trends in effectiveness.
Tertiary/Exploratory		
Determine the effectiveness of promoting pharmacist-prescriber collaboration in new DOAC prescriptions through the design of CDS alerts	The difference in outcome measures (primary and secondary outcomes) between Notification A and B conditions	While alerts are expected to reduce prescription errors, variations in alert and design to encourage pharmacy collaboration may provide added benefit

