**Implementation** (including fidelity): To address how various EHR alerts impact implementation of evidence-based DOAC prescribing, we examine process measures related to prescriber and pharmacist alert receipt. For prescribers, we will examine how often they order (or do not order) the medication recommended by the alerts (and, for the latter, whether they provide a reason) for both new-prescription alerts and existing-prescription notifications. For pharmacists, we will measure how often they respond to referrals at the time of initial prescribing or to existing prescription notifications, as well as the time from referral/alert until the pharmacist documents a recommendation in the EHR. For existing prescription notifications, we also will measure the time from notification until the notification is read as well as time until any DOAC prescription change or related EHR documentation occurs as well as the number of times a existing-prescription notification is read before being acted on.

**Maintenance:** To measure maintenance and sustainment, we will assess all “reach” and “adoption” outcomes after 6 and 12 months for all patients, and after 18 months for the subset of prescribers enrolled prior to the second quarter of Year 2 (approximately N=225, or 75% of the total prescriber enrollment). This will also allow us to investigate whether treatment effects for prescribers are maintained after the initial adoption.

**Other implementation outcomes:** We will also estimate the resource utilization by the pharmacists using a combination of EHR tool tracking (measured in hours) and self-reported weekly hours dedicated to study activities using a study provided tracking sheet similar to those used in our prior implementation trials (R01MH099898; R01MH114023).

---

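### The 94% power in Section 9.1 is not conservative for the 18-month comparison in about 225 prescribers, nor for a test of whether the treatment effect is maintained

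*Combined protocol and SAP*

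**What the plan says.** Section 9.1 states: "For our secondary prescriber-level outcomes, we will have 94% power to detect a difference in proportions of 0.4 to 0.6". The next sentence extends this figure: "For longitudinal outcomes (e.g., maintenance), this calculation is conservative as it does not account for repeated measures". Maintenance is thus the plan's own example of an outcome for which 94% is offered as a floor.

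Section 9.3.4 (Maintenance) describes what will be assessed. Reach and adoption outcomes are examined at 6 and 12 months for all patients. The last look covers only part of the sample: "after 18 months for the subset of prescribers enrolled prior to the second quarter of Year 2 (approximately N=225, or 75% of the total prescriber". The same paragraph says this will show whether treatment effects persist after the initial adoption.

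Section 3 lists as a secondary endpoint "Change in magnitude of effect for the existing-prescription notification over time", and a matching endpoint for the new-prescription alerts. Both are to be reported for the institution, not for individuals.

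No power figure is given for the 225-prescriber subset or for any change in effect. No correlation between a prescriber's outcomes at different times is stated.

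**The concern.** Calling a power figure conservative promises that the true power is at least that high. The promise depends on the quantity being estimated. Repeated measures sharpen an effect averaged over time. They do not restore prescribers missing from a single late comparison, and they do not turn the power for one difference into the power for a difference between two differences.

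With 94% on record as a floor, a non-significant change in effect could be taken as good evidence that the effect lasted. At low correlation the design would usually miss a halving of the effect. The documents do not say that they will draw this inference, but the sentence in Section 9.1 invites it.

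**Working it through.** **Inputs**
- Proportions 0.40 and 0.60, with 94% power (Section 9.1).
- 150 prescribers per arm: "allowing for a main effect comparison of 150 prescribers randomized to each of Notification A vs. B" (Section 9.1, and likewise for the two alerts).
- "alpha of 0.05 and prescriber-level ICC of 0.1" (Section 9.1, stated for the primary calculation). The two-sided test is stated in Section 9.1 for the moderator analyses. Both are assumed to apply to the 94%.
- About 225 prescribers at 18 months, so 225/2 = 112.5 per arm (Section 9.3.4).
- An average of 2 triggering patients per prescriber in 12 months (Section 9.1).
- Correlation over time within a prescriber: not given. Assumed range 0 to 0.5. The ICC of 0.1 is between patients of one prescriber and serves only as a reference value.

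**Step 1. Reproduce the 94%.** Power = Φ[(d − 1.96·√(2·0.25/n)) / √(2·0.24/n)], with d = 0.20.
- n = 150: (0.20 − 1.96 × 0.0577)/0.0566 = 1.535, so 93.8%. With unpooled variance it is 94.2%.

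The figure is one cross-sectional comparison with one outcome per prescriber.

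**Step 2. The 18-month subset.** Same formula, n = 112.5: (0.20 − 1.96 × 0.0667)/0.0653 = 1.061, so 85.6%. The chance of missing the effect rises from about 6% to about 14%.

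**Step 3. Where the claim is right.** For an effect averaged over two measures per prescriber, variance = (0.48/n)·(1 + ρ)/2.
- n = 150: 99.9% at ρ = 0, 99.8% at 0.1, 98.3% at 0.5.
- n = 112.5: 99.1%, 98.5% and 94.2%.

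**Step 4. A change in effect between arms.** Assumed model: two periods, one event per prescriber in each, binary variance 0.24 throughout. The variance of the difference between the two arm differences is 4 × 0.24 × (1 − ρ)/n = 0.96(1 − ρ)/n. Power = Φ(change/SE − 1.96). The smallest change detectable with 80% power is 2.80 × SE.

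Example, n = 150 and ρ = 0.1: SE = √(0.96 × 0.9/150) = 0.0759. For a change of 0.20, 2.635 − 1.96 = 0.675, so 75.0%. For 0.10, 1.318 − 1.96 = −0.642, so 26.0%. Smallest detectable change: 2.80 × 0.0759 = 0.213.

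| ρ | 300 prescribers: 20 to 0 points | 20 to 10 points | smallest change (points) | 225 prescribers: 20 to 0 points | 20 to 10 points | smallest change (points) |
|---|---|---|---|---|---|---|
| 0 | 70.5% | 23.9% | 22.4 | 58.1% | 19.0% | 25.9 |
| 0.1 | 75.0% | 26.0% | 21.3 | 62.6% | 20.6% | 24.6 |
| 0.3 | 84.8% | 32.1% | 18.8 | 73.5% | 25.3% | 21.7 |
| 0.5 | 94.2% | 42.4% | 15.8 | 86.5% | 33.4% | 18.3 |

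Power for complete loss reaches 94% only at ρ of about 0.49 with 300 prescribers, or 0.62 with 225.

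**Step 5. More events.** At 3 events per prescriber (900 in all, 225 per arm and period, treated as independent), SE = √(0.96/225) = 0.0653. Power is 86.5% for complete loss and 33.4% for a halving.

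**The case against.** The strongest defence is that the sentence is correct on its natural reading. It gives repeated measures as its reason, and for a time-averaged effect the reason holds: Step 3 shows at least 98% with all 300 prescribers up to ρ = 0.5. This stands, so the sentence should be narrowed and not struck out.

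Other readings are tempting but go further than the documents allow:

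- A reader might infer that every maintenance outcome relies on a subset or on a change in effect. Section 9.3.4 covers all patients at 6 and 12 months. If all 300 prescribers contribute at such a time point, 94% applies unchanged.
- A reader might treat the change-over-time endpoints in Section 3 as arm-by-time contrasts. They are reported at institution level, and Section 3 puts the comparisons between conditions in separate exploratory rows. An institution-level trend need not compare arms. The arm-by-time reading is better supported by Section 9.3.4, which asks about persistence of treatment effects.
- A reader might spread 2 events per prescriber over the whole 18 months. Section 9.1 gives 2 per 12 months. At that rate a prescriber followed for 18 months would have about 3, although entry is staggered. Step 5 shows that 3 events still leave power below 94%.
- A reader might take 75% or 21 points as settled figures. They depend on an assumed two-period model and on a correlation that the documents do not give.

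It is also fair to say that Section 8.2 calls these implementation outcomes exploratory, and that Section 9.1 powers the study on the primary comparison. Neither the sample size nor the primary inference depends on the sentence.

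**Conclusion.** The sentence is wrong as written, within limits. The 94% is the power of one comparison between 150 and 150 prescribers. It is conservative only for a time-averaged treatment effect.

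For a single 18-month comparison in the plan's own subset, power is about 86%, some 8 points lower. This result needs no assumption beyond equal arms and the test that reproduces the 94%.

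For whether the treatment effect is maintained, and for the Section 3 endpoints if they are analysed between arms, 94% is not a lower bound. With all 300 prescribers, power for complete loss of a 20-point effect is 71%, 75%, 85% and 94% at correlations of 0, 0.1, 0.3 and 0.5. For a halving it is 24% to 42%. These figures rest on the assumed model of one event per prescriber in each of two periods. How far power falls short depends on the unstated correlation, and for complete loss the shortfall closes at about 0.5. The primary analysis is unaffected.

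**What to change.** In Section 9.1:
- Limit the word conservative to treatment effects averaged over time in all 300 prescribers.
- State about 86% power for a single 18-month comparison of 0.40 with 0.60 in the subset of about 225.
- State that a test of effect by time has lower power, and give the smallest detectable change together with its assumptions. Under the two-period model with 300 prescribers this is about 16 to 22 points for correlations from 0.5 to 0, and about 21 at 0.1.

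In Section 3 or 9.3.4, say whether the institution-level change-over-time endpoints are compared between arms. In Section 9.3.4, commit to reporting the change in effect with its confidence interval, and do not take a non-significant result as evidence of maintenance.

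The cost is a few sentences and a less favourable stated figure. No further data, prescribers or patients are needed.

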### 9.3.4 ANALYSES OF IMPLEMENTATION

**Reach:** To assess reach, we will examine the proportion of patients on DOACs that had alerts or notifications fire, as well as the proportion of prescribers that received alerts and/or notifications. To further understand reach, we will also report the proportion and clinical predictors of prescribers who dismissed alerts or notifications (defined as no action within seven calendar days). We will also identify the proportion and predictors of prescribers who used anticoagulation clinic pharmacist referrals in new-prescription alerts. We will also categorize all DOAC alerts based on prescriber and patient characteristics (e.g., demographics, comorbidities).

**Effectiveness:** Analysis of Effectiveness will be the focus of the primary and secondary outcome measures (as noted above). We will evaluate the effectiveness of our DOAC alert system components by examining patient-level clinical adverse event rates (bleeding and thrombotic) within 30 days of triggering the alert. This time period was selected to minimize potential contamination from the safety review mechanism described above, and we recognize that rates for the adverse events will be low.

However, as a T4 implementation study, the primary goal is implementing the evidence-based practice for which efficacy is already established. Supplementary analyses will also examine the effect of the alert system overall on adverse events.

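### The 63% and 79% power stated for adverse-event rates of 1% vs 0.5% cannot come from the stated inputs, which give about 11% and 13%; the stated figures match 10% vs 5%.

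*Combined protocol and SAP*

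**What the plan says.** Section 9.1 gives a numerical power for what it calls the clinical effectiveness secondary outcome, the rate of bleeding and thrombotic events: "we will have 63% power to detect a difference of 1% vs. 0.5% in adverse event rates for each factor". The inputs given beside it are "again assuming 300 prescribers with an average of 2 patients each" and a prescriber-level ICC of 0.03. It then adds "A less conservative estimate of 3 patients per prescriber increases this power to 79" (per cent).

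The allocation appears earlier in the same section. For notifications, the plan describes "allowing for a main effect comparison of 150 prescribers randomized to each of Notification A vs. B"; for alerts, 300 prescribers, "or 150 to each of Alert 1 and Alert 2, respectively". The primary calculation uses "alpha of 0.05 and prescriber-level ICC of 0.1". Section 9.1 mentions a two-sided test only for the moderator analyses.

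Section 9.3.4 commits the trial to this outcome: "We will evaluate the effectiveness of our DOAC alert system components by examining patient-level clinical adverse event rates", within 30 days of the trigger. Sections 8.1 and 9.3.4 say that event rates are expected to be low. No other adverse-event rate, and no larger sample for this outcome, appears in the document.

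**The concern.** The expected event counts alone make the statement implausible. With 300 patients per arm, rates of 1% and 0.5% mean about 3 events against 1.5. No standard test separates two such counts nearly two times in three.

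What is at stake is how the result will be read. A stated power of 63% to 79% suggests a comparison that is moderately informative even after allowing for low rates. Readers, or the DSMB, could then take a non-significant difference in bleeding or thrombosis as some evidence that the arms are equally safe. Harm is a live question in this trial: Section 8.4.2.2 asks whether the 15-day dashboard embargo contributed to patient harm, and Section 9.3.6 allows the trial to be halted if events differ between arms at p < 0.01.

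**Working it through.** **Inputs (all Section 9.1).** 150 prescribers per arm for each factor; m = 2 or 3 patients per prescriber; ICC 0.03; rates 1% and 0.5%. Alpha of 0.05 and a two-sided test are not restated for this outcome, so they are carried over as assumptions.

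**Formulas.**
- Effective patients per arm: n = 150m / (1 + (m − 1) × ICC).
- Two-proportion z-test with pooled null variance: power = Φ[(|p1 − p2| − 1.96·SE0) / SE1], plus the very small opposite tail. Here SE0 = √(2·p̄(1 − p̄)/n) and SE1 = √([p1(1 − p1) + p2(1 − p2)]/n).

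**Step 1: check the method against other figures in Section 9.1.**

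| Comparison | Recomputed | Stated |
|---|---|---|
| 40% vs 52%, m = 2, ICC 0.1 (n = 300/1.1 = 272.7) | 80.5% | 80% |
| 0.4 vs 0.6, 150 prescribers per arm | 93.8% | 94% |
| Table 3, m = 2, RR 1.2, base 0.3 / 0.4 / 0.5 / 0.6 | 31.9 / 46.9 / 65.1 / 84.3% | 32 / 47 / 65 / 84% |

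The method reproduces these figures, so it appears to be the plan's own.

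**Step 2: apply it to 1% vs 0.5%.**
- m = 2: n = 300/1.03 = 291.3. SE0 = 0.00715 and SE1 = 0.00715. (0.005 − 1.96 × 0.00715)/0.00715 = −1.26, giving 10.4%, or **10.8%** counting both tails. Stated: 63%.
- m = 3: n = 450/1.06 = 424.5. SE0 = 0.00592 and SE1 = 0.00592. (0.005 − 1.96 × 0.00592)/0.00592 = −1.12, giving 13.2%, or **13.5%** counting both tails. Stated: 79%.

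**Step 3: change the assumptions one at a time.**

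| Variant | m = 2 | m = 3 |
|---|---|---|
| One-sided 0.05 | 17.2% | 21.2% |
| ICC 0 | 10.9% | 14.0% |
| 300 prescribers per arm | 16.7% | 22.3% |
| Two-sided alpha 0.20 | 30.4% | 34.8% |
| Fisher's exact test, clustering ignored (300 and 450 per arm) | 2.3% | 5.7% |

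None comes near 63% and 79%.

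**Step 4: look for rates that do give the stated figures.** For 10% vs 5%, all else unchanged:
- m = 2: SE0 = 0.02183 and SE1 = 0.02173. (0.05 − 1.96 × 0.02183)/0.02173 = 0.33, giving **63.0%**.
- m = 3: SE0 = 0.01808 and SE1 = 0.01800. (0.05 − 1.96 × 0.01808)/0.01800 = 0.81, giving **79.1%**.

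Both match the stated values to the rounded percent.

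**Step 5: what the design can do.**
- At 80% power and m = 2, it detects about 1% vs 4.9%, or 0.5% vs 3.9%. At m = 3, it detects about 1% vs 4.0%.
- If the true rates were 1% and 0.5%, the 95% interval for the risk difference at m = 2 would be about ±1.96 × 0.00715 = ±1.4 percentage points around a difference of 0.5.
- Power of 63% for 1% vs 0.5% needs about 3,128 independent patients per arm. At m = 2 that is 3,128 × 1.03/2 ≈ 1,611 prescribers per arm. Section 9.1 puts the institution's DOAC prescribers at a little over 1,000 in total.

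**The case against.** The arithmetic is not in dispute. The case on the other side concerns cause, weight and remedy.

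- **Cause.** The tenfold slip is an inference. Other pairs, such as about 0.5% vs 3.0% or 1% vs 3.95%, also give roughly 63% and 79%. This stands, so the right wording is that the figures are consistent with 10% vs 5%. That pair is the most plausible because it keeps the stated 2:1 ratio. Whatever the cause, 63% and 79% are wrong for 1% vs 0.5%.
- **Weight.** The trial is powered on prescription change, and that calculation reproduces. Adverse events did not set the sample size and are not in the Section 3 endpoint table. Section 9.3.4 puts implementation first, and Section 9.3.6 makes the safety presentations descriptive. These points limit the consequences. They do not make the figures right, and Section 9.1 itself names this a secondary outcome.
- **Misreading.** The plan nowhere says that a null result would be taken as equal safety; 63% is already below the usual 80%; and low rates are acknowledged. That is fair, but a numerical power suggests that the low rates have been allowed for. Low expected rates also sit poorly with a 10% vs 5% scenario.
- **Planning inputs.** The 300 prescribers are a minimum, and the average of 2 patients refers to 12 months of an 18-month trial. Actual numbers may be higher. Doubling the prescribers gives only 16.7% and 22.3%.
- **Remedy.** Section 9.3.4 contains no arithmetic error. Changing it is advisable rather than required.

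**Conclusion.** The concern holds. Under the plan's own inputs, with two-sided alpha of 0.05 carried over, power for 1% vs 0.5% is about 11% with 2 patients per prescriber and 13% with 3. The stated 63% and 79% overstate it about sixfold (63/10.8 = 5.8; 79/13.5 = 5.9). Changing the alpha, sidedness, ICC or number of prescribers as in Step 3 does not recover the stated values. The explanation by 10% vs 5% is strongly supported but not proven. The error is confined to a secondary outcome and leaves the sample size and primary analysis as they are. Even so, it attributes to a harm comparison a sensitivity that the trial does not have.

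**What to change.** In Section 9.1, do one of the following:

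1. Keep 1% vs 0.5% and replace 63% and 79% with about 11% and 13%, stating the alpha, sidedness and test; or
2. State the rates that were actually entered (10% vs 5%, if the Stata input confirms this) and justify them against the expectation of low rates.

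Either way, add the difference detectable at 80% power under the stated assumptions: about 1% vs 4.9% with 2 patients per prescriber, and 1% vs 4.0% with 3.

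It would also help if Section 9.3.4 presented the adverse-event comparison as estimation (a risk difference with a cluster-adjusted 95% confidence interval) and said that a non-significant result does not show equal safety.

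The cost is a wording amendment and a less favourable power statement. No participants, data collection or primary analysis change.
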